12.1 Variable derivation

Table 3: Variable derivation rules

Parameter	Calculation
Screened	A patient is considered screened if (s)he has “Has written Informed Consent been obtained?” = Yes AND “Date of Informed Consent Signature at screening” filled
Screening failure	A patient is considered screening failure if (s)he has “Screen Failure date” filled
Enrolled	A patient is considered enrolled if (s)he has been screened and (s)he is not a screening failure.
Eligible eye	Assuming that all the inclusion/exclusion criteria are met: 
• If only one eye fulfills the criteria of Severe Sjögren's Dry Eye (“Which eye is diagnosed with Severe Sjögren's Dry Eye?” is answered with “Right Eye” or “Left Eye”) than the selected eye will be the “eligible eye”.• If both eyes fulfill the criteria of Severe Sjögren's Dry Eye (“Which eye is diagnosed with Severe Sjögren's Dry Eye?” is answered with “Both”) than the eligible eye will be selected according to the following rank:
i. the eye with lower Schirmer I score, otherwiseii. the eye with worse NEI score (cornea+conjunctival staining), otherwiseiii. the eye with worse investigator's judgement (“Were there any clinically significant abnormalities noted?” Equal to yes for a specific eye), otherwiseiv. the right eye.
Change from baseline	Each change from baseline will be defined as difference between the value at each post-baseline assessment and the baseline value.
Time since first diagnosis of Dry Eye	Randomization date - Date of diagnosis for eligible eye + 1

Parameter	Calculation
Time since first diagnosis of Severe Sjögren's Dry Eye	Randomization date - Date of diagnosis of Severe Sjögren's Dry Eye for eligible eye + 1
Total number of drops in the eligible eye taken during the treatment period	Sum of Morning/Afternoon/Evening Number of times the IMP has been administered for the eligible eye between Randomization visit date and End of Treatment date, considering 1 drop each time (morning, afternoon, evening). (from the eCRF form "IMP Administration" forms)
Total number of drops in the eligible eye scheduled during the treatment period	3*(Date of End of Treatment visit – Date of Randomization + 1) – (assessments not done on Randomization visit + assessments not done on End of Treatment visit)
The extent of exposure (days)	Date of last administration of IMP – Date of first administration of IMP + 1
Total number of drops of the preservative free artificial tears during the treatment period	Sum of Morning/Afternoon/Evening Number of drops taken for eligible eye between Randomization visit date and End of Treatment date. (from the eCRF form "Frequency of preservative free artificial tears use" forms)
Total number of days of the treatment period	End of Treatment date – Randomization date + 1
Total number of drops of the preservative free artificial tears during the follow-up period	Sum of Morning/Afternoon/Evening Number of drops taken after End of Treatment date. (from the eCRF form "Frequency of preservative free artificial tears use" forms)
Total number of days of the follow-up period	Last follow-up available visit* date – End of Treatment date + 1 (* with assessment of Frequency of preservative free artificial tears use)
Time from randomization to study discontinuation (days)	End of Study date – Randomization date + 1

Parameter	Calculation
Primary Sjögren's	For the subgroup analyses, a patient will be classified in the primary Sjögren's syndrome if the patient experienced any previous and/or concomitant ocular with diagnosis= 'Sjögren Syndrome'
Conversion of Time Intervals	If a time interval was calculated in minutes, hours or days and needs to be converted into months or year the following conversion factors will be used: 
• 1 hour = 60 minutes• 1 day = 24 hours• 1 week = 7 days• 1 month = 30.4375 days• 1 year = 365.25 days
General rule	For calculation of a time interval, in case time is available, it is considered in the formula. Time intervals will be expressed in hours in if less than 24 hours and days if more than 24 hours.

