4.1. INCLUSION CRITERIA

To be eligible for inclusion into this study, each patient must fulfil the following inclusion criteria:

1. Male or female aged ≥ 18 years
2. Patients with a confirmed diagnosis of Sjögren's syndrome or other autoimmune disease known to induce Sjögren's Dry Eye Disease (DED).
3. Patients with severe Sjögren's dry eye disease characterized by the following clinical features:
 - a. Corneal and/or conjunctival staining with fluorescein using National Eye Institute (NEI) grading system ≥ 3
 - b. SANDE questionnaire >25 mm
 - c. Schirmer test I (without anaesthesia) $\geq 2 \leq 5$ mm/5min
4. The same eye (eligible eye) must fulfill all the above criteria
5. Patients diagnosed with severe Sjögren's dry eye disease at least 3 months before enrolment (current use or recommended use of artificial tears for the treatment of Sjögren's related Dry Eye)
6. Best corrected distance visual acuity (BCDVA) score of ≥ 0.1 decimal units (20/200 Snellen value) in each eye at the time of study enrolment
7. If a female of childbearing potential, have a negative urine pregnancy test and use a highly effective method to avoid pregnancy for the duration of the trial and 30 days after the study treatment period. Males of reproductive potential should use effective contraception during treatment and 30 days after the study treatment period.
8. Only patients who satisfy all Informed Consent requirements may be included in the study. The patient and/or his/her legal representative must read, sign and date the Informed Consent document before any study-related procedures are performed. The Informed Consent form signed by patients and/or legal representative must have been approved by the IRB/IEC for the current study
9. Patients must have the ability and willingness to comply with study procedures

EXCLUSION CRITERIA

1. Inability to speak and understand the local language sufficiently to understand the nature of the study, to provide written informed consent, and to allow the completion of all study assessments
2. Evidence of an active ocular infection, in either eye
3. Presence of any other ocular disorder or condition requiring topical medication during the entire duration of study in either eye

4. History of severe systemic allergy or of ocular allergy (including seasonal conjunctivitis) or chronic conjunctivitis and/or keratitis other than dry eye
5. Intraocular inflammation defined as Tyndall score >0
6. History of malignancy in the last 5 years

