4.7 Eligible eye

Assuming that all the inclusion/exclusion criteria are met in both eyes, the worse eye (eligible eye) will be determined at the baseline visit using a stepladder approach, as follows:

1. Schirmer’s Test: worse eye determined as eye with lower Schirmer I score.
2. NEI score: if Schirmer I score is the same in both eyes, worse eye will be determined by NEI score (cornea + conjunctival staining).

If all the above are identical, determination of the worse eye will be based on the investigator’s judgement, otherwise the right eye will be used as the eligible eye.

5. Sample size justification

The sample size of the study is calculated based on results from previous studies.

Sample size was calculated according to the following assumptions:

- randomization ratio 1:1.
- a difference of 30% in Schirmer I rate of responders (value >10mm/5min at week 4.) in favor of rhNGF treatment at Week 4, with a responder rate of 5% for vehicle.
- 15 points in Global SANDE score improvement at Week 12, with a standard deviation of 20 points.

Based on these assumptions, a total sample size of 90 evaluable patients (100 pts considering 10% of patients not evaluable after enrollment) allows to achieve an overall power of 90% to show superiority of rhNGF eye drops solution vs vehicle in terms of both co-primary endpoints, considering a one-sided alpha of 0.025. Specifically:

- A power of 95.8% is achieved for Schirmer I primary endpoint.
- A power of 94.0% is achieved for SANDE primary endpoint.

6. Randomization and blinding

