8.7 Dry Eye History

The dry eye history characteristics will be summarized by treatment and overall, by means of descriptive statistics. No statistical testing will be carried out. The following information will be reported:

- Eye affected by Dry Eye.
- Time since first diagnosis of Dry Eye.
- Has the patient received prior treatment for dry eye?
- Eye diagnosed with Severe Sjögren's Dry Eye.
- Time since first diagnosis of Severe Sjögren's Dry Eye.

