8.8.1 Eligible eye

Eye which is defined as eligible eye and the used criteria (IE, Worst Schirmer's test, Worst NEI score, investigator's judgement, right as per protocol rule) will be reported.

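### SAP Table 3 chooses the analysed eye from a diagnosis question and does not check each eye's baseline values, so the Schirmer co-primary can be read in an eye that fails the entry criteria

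*SAP*

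**What the plan says.** **Entry.** Protocol 4.1, criterion 3, sets staining (3a, NEI at least 3), symptoms (3b) and Schirmer I between 2 and 5 mm inclusive (3c). Criterion 4 adds: "The same eye (eligible eye) must fulfill all the above criteria". One qualifying eye is enough; the fellow eye need not qualify. Criterion 5 is a separate history requirement: "Patients diagnosed with severe Sjögren's dry eye disease at least 3 months before enrolment".

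**Choice of eye in the protocol and SAP text.** SAP 4.7 repeats Protocol 4.2: "Assuming that all the inclusion/exclusion criteria are met in both eyes, the worse eye (eligible eye) will be determined at the baseline visit". The order is lower Schirmer I, then worse NEI, then investigator's judgement, then the right eye.

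**Choice of eye in the derivation.** In SAP 12.1, Table 3, the lead-in assumes that the entry criteria are met but does not say in both eyes. Two branches follow, for one eye or both eyes fulfilling the criteria of severe Sjögren's dry eye. In each branch a parenthesis ties the condition to the answer to the question on which eye has that diagnosis. If the answer is *Both*, "than the eligible eye will be selected according to the following rank", and the first rank is the lower Schirmer I.

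**Related places.** SAP 8.7 reports the diagnosis item ("Eye diagnosed with Severe" Sjögren's dry eye) under Dry Eye History. SAP 8.8.1 reports "Eye which is defined as eligible eye and the used criteria (IE", followed by the four ranks). SAP 7.9, which lists changes from the protocol, does not mention eye selection. The protocol synopsis defines the Schirmer co-primary in the eligible eye.

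**The concern.** Table 3 is the rule a programmer will code, and the variable that decides its branch is a diagnosis made at least three months before enrolment. That answer cannot certify what each eye measured at baseline. Sjögren's disease may well be diagnosed in both eyes when only one has Schirmer I of 2 to 5 mm together with NEI of at least 3. The ranking then favours the lower Schirmer with no 2 mm floor and no NEI threshold, so it can move the analysis from the qualifying eye to the non-qualifying one.

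At stake is which eye supplies the binary outcome of a co-primary endpoint. In whole millimetres, an eye at 0 or 1 mm must gain 10 or 11 mm to exceed 10 mm; an eye at 2 to 5 mm must gain 6 to 9 mm. The baseline Schirmer value, a covariate in the SAP 10.1.2.1 model, would also fall outside its entry range. Other endpoints analysed in the eligible eye would follow the same selection.

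**Working it through.** **1. The plan's own figure.** Inputs from SAP section 5: 45 evaluable patients per arm (90 at 1:1), responder rates 5% on vehicle and 35% on cenegermin (5% plus 30 points), one-sided alpha 0.025. With pooled variance under the null,

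z = [d√n − 1.960·√(2·p̄·(1−p̄))] / √(p1(1−p1) + p2(1−p2))

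= [0.30 × 6.708 − 1.960 × √0.32] / √0.275 = (2.012 − 1.109) / 0.524 = 1.723.

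Power is 95.8%, as stated. With the stated 94.0% for SANDE, 0.958 × 0.940 = 0.901, which matches the stated overall 90%.

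**2. Can the rule select a non-qualifying eye?** Take whole-millimetre values from 0 to 10 in each eye, both eyes diagnosed and NEI adequate in both.
- Pairs with at least one eye at 2 to 5 mm: 11² − 7² = 72.
- Pairs in which the lower eye is outside 2 to 5 mm: one eye at 0 or 1 and the other at 2 to 5, so 2 × 2 × 4 = 16. The selected value is always 0 or 1 mm.
- If the ranking is limited to eyes that qualify on their own values: 0 of 72.

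This count shows that the rule can fail and in which direction; it is not a frequency. On this branch the selected eye cannot exceed 5 mm. Separately, the lower-Schirmer eye may have NEI below 3. On the one-eye branch, the only diagnosed eye need not be the eye that met criteria 3a and 3c.

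**3. Example.** Both eyes diagnosed; left 4 mm with NEI 5, right 1 mm. Criterion 4 is met by the left eye only. Under Protocol 4.2 and SAP 4.7 the ranking does not apply, because the right eye fails 3c. Under Table 3 the answer *Both* triggers it, and the right eye is selected.

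**4. Bounding case for power.** Assume a fraction f of patients in each arm is analysed in such an eye, none of those eyes responds in either arm, and everyone else responds at the planned rates. The rates become 0.35(1−f) and 0.05(1−f), put into the same formula:

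| f | Cenegermin | Vehicle | z | Schirmer power | × 0.940 |
|---|---|---|---|---|---|
| 0 | 35.0% | 5.0% | 1.723 | 95.8% | 90.0% |
| 5% | 33.25% | 4.75% | 1.595 | 94.5% | 88.8% |
| 10% | 31.5% | 4.5% | 1.467 | 92.9% | 87.3% |
| 20% | 28.0% | 4.0% | 1.212 | 88.7% | 83.4% |

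The values of f and the zero response are assumptions; neither comes from the documents. The last column uses unrounded Schirmer power and the simple product that reproduces the plan's overall figure.

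**The case against.** The strongest defence is that Table 3 already says the right thing. It assumes the entry criteria are met and speaks of one or both eyes fulfilling the criteria of severe disease. Criterion 3 itself describes severe disease through the staining, symptom and Schirmer thresholds. Read that way, an eye at 1 mm does not fulfil the criteria and the ranking is never reached. This is a fair reading of intent. It does not rescue the operational rule: the parenthesis turns the condition into the diagnosis answer, and the lead-in can be satisfied by one eye.

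Second, the failure depends on how sites answer the question. The case report form is cited but not shown, and sites may answer *Both* only when each eye meets criterion 3. This stands, and it limits both confidence and severity.

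Third, a reader might infer from the IE reason in SAP 8.8.1 that Table 3 has lost a step. That does not follow: IE can correspond to Table 3's first branch, where only one eye fulfils the criteria. What is missing is a check on measured values.

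Fourth, a reader might estimate how many patients are affected by modelling the fellow eye. The documents give no fellow-eye data, and the answer follows the assumptions. A normal model (mean 3 to 5 mm, SD 3, between-eye correlation 0.5 to 0.9) gives 13% to 36% of eligible patients. Two log-normal settings (median 5, log-SD 0.6, correlation 0.85; and median 3, log-SD 0.8, correlation 0.5) give 8.0% and 35.4% with rounding down, or 3.5% and 25.3% with rounding to the nearest millimetre. All of these suppose that *Both* is answered in every such patient, so none is usable as a frequency.

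**Conclusion.** The point holds as a faulty operational rule. Coded as written, Table 3 can place an eye at 0 or 1 mm, or one with NEI below 3, into the Schirmer co-primary. This departs from criterion 4, Protocol 4.2 and SAP 4.7 and is not declared in SAP 7.9.

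Its size is unknown, because it depends on the two eyes' baseline values and on site practice in answering the diagnosis question. The power losses above are bounds under a no-response assumption, not predictions; a lower response in such eyes is plausible, but the documents do not demonstrate it.

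Two stronger inferences are not supported. Type I error is not inflated, because selection uses baseline data and the same rule in both arms. The SANDE co-primary is a patient-level score and is not affected. SHOULD-FIX, moderate confidence.

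**What to change.** Before unblinding, amend the eligible-eye entry of Table 3 as follows:

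1. Flag each eye as qualifying when its own baseline values meet 3a and 3c (NEI at least 3, Schirmer I 2 to 5 mm).
2. If exactly one eye qualifies, use it, whatever the diagnosis answer.
3. Apply the existing ranking only if both eyes qualify.
4. If neither eye qualifies (a patient randomised in error), apply the same ranking to both eyes. The FAS in SAP 7.2.4 keeps every randomised and treated patient, so each needs an analysed eye.
5. State which NEI source is used for eye selection, and reconcile it with the reading-centre priority in SAP 7.8, given that the eye is to be determined at the baseline visit.
6. List every patient whose derived eye disagrees with the diagnosis answer, or with the site's designated eye if that is recorded, and resolve these at the blind data review (SAP 7.10).

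Align SAP 4.7 and 8.8.1 with the new text. The cost is one table entry and one programmed check on baseline Schirmer and NEI values that the protocol already collects in both eyes. Whether the site's designation has its own field cannot be seen from the documents, so item 6 must work without it. The stated sample size and power figures do not change.

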9.3 Use of preservative free artificial tears

The use (n° drops/day) of preservative free artificial tears will be summarized with descriptive statistics by treatment group and overall, by study period (treatment / follow-up) and overall according to the following formulas:

$$\text{Use}_{TREAT} = \frac{\text{total number of drops of the preservative free artificial tears during the treatment period}}{\text{total number of days of the treatment period}} \times 100$$

$$\text{Use}_{F-UP} = \frac{\text{total number of drops of the preservative free artificial tears during the follow-up period}}{\text{total number of days of the follow-up period}} \times 100$$

Details are provided in Table 3.

10. Evaluation of Efficacy

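### SAP 9.3 multiplies artificial-tear drops per day by 100, and Table 3 names no eye for follow-up and counts one follow-up day too many; only descriptive tables are affected

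*SAP*

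**What the plan says.** SAP 9.3 sets the unit and layout: "The use (n° drops/day) of preservative free artificial tears will be summarized with descriptive statistics by treatment group and overall, by study period". It then displays one formula for the treatment period and one for follow-up. Each is total drops over total days, followed by a multiplication by 100, and the section refers to Table 3 for details.

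SAP 12.1, Table 3, defines the four components:

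- Treatment-period drops: "Sum of Morning/Afternoon/Evening Number of drops taken for eligible eye between Randomization visit date and End of Treatment date".
- Treatment-period days: "End of Treatment date – Randomization date + 1".
- Follow-up drops: "Sum of Morning/Afternoon/Evening Number of drops taken after End of Treatment date".
- Follow-up days: "Last follow-up available visit* date – End of Treatment date + 1", where the asterisk restricts this to visits at which tear use was assessed.

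The results go into Tables 14.3.2.3.1 (FAS) and 14.3.2.3.2 (SAF).

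The tear regimen changes over the study. Under protocol 5.1.1 and 5.6, tears are taken only as needed during the 4 treatment weeks. In the first 8 weeks of follow-up they are scheduled three times daily in both eyes, with extra drops as needed. Under protocol 3.3, other topical treatments are allowed after week 12.

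**The concern.** Three details in the definitions do not fit together.

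1. **Unit.** A rate in drops per day has no percentage reading, so the factor 100 contradicts the stated unit. It does belong in the IMP compliance formula in SAP 9.1, which is a true percentage of scheduled drops taken.
2. **Eye.** One numerator is limited to the eligible eye and the other is not. Tears go into both eyes, and the protocol asks patients to record additional drops for each eye. A programmer following the text literally could sum both eyes in follow-up.
3. **Dates.** The End of Treatment day is in the day count of both periods, but its drops are counted only in the treatment period.

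These two tables are the planned summaries of tear use by arm. Lubrication in weeks 5-12 is useful context for the week 12 SANDE co-primary endpoint, because the treatment-policy estimand (SAP 7.3) takes all observed values as they are. If the SAP is followed exactly, the printed values do not match their unit, and a shift between periods could come from the definition alone.

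**Working it through.** The documents give no numerical result for tear use, so there is no figure to reproduce. The check applies the formulas as written to a patient whose use never changes.

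**Inputs**

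- Nominal days from the visit schedule: randomization day 1, End of Treatment day 28, week 12 day 84, week 24 day 168.
- Assumed rate: 3 drops/day in each eye throughout. This equals the scheduled follow-up regimen. For the as-needed treatment period it is purely illustrative.

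**Treatment period (eligible eye, as Table 3 states)**

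- Drops: 3 × 28 = 84. Days: 28 − 1 + 1 = 28.
- As written: 84 / 28 × 100 = **300**. In the stated unit: 84 / 28 = 3.00.

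**Follow-up, last tear-use visit at week 12**

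- Days on which drops count: 84 − 28 = 56. Days in the denominator: 84 − 28 + 1 = 57.
- Eligible eye: 3 × 56 = 168 drops; 168 / 57 × 100 = **294.7**.
- Both eyes: 336 drops; 336 / 57 × 100 = **589.5**.

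**Follow-up, last tear-use visit at week 24**

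- Days on which drops count: 168 − 28 = 140. Days in the denominator: 141.
- Eligible eye: 420 / 141 × 100 = **297.9**.
- Both eyes: 840 / 141 × 100 = **595.7**.

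**Size of each part**

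| Part | Effect |
|---|---|
| Factor 100 | exactly 100-fold, same in both arms and both periods |
| Eye not named | none if the eligible eye is used; 2-fold if both eyes are summed |
| Extra day | 1/57 = 1.8% too low to week 12; 1/141 = 0.7% to week 24 |

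To week 12, the follow-up/treatment ratio for this patient is 294.7 / 300 = 0.98 or 589.5 / 300 = 1.97, although actual use did not change.

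**After correction** (no factor 100, eligible eye in both rows, no +1): 84 / 28 = 3.00, 168 / 56 = 3.00 and 420 / 140 = 3.00.

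**Pooling, as a separate matter.** Suppose, as an assumption, that a patient takes 3 drops/day in the eligible eye in weeks 5-12 and none afterwards. Even with the formula corrected, pooled follow-up gives 168 / 140 = 1.20 drops/day, while use before the week 12 SANDE assessment was 3.00. This is a loss of information, not an arithmetic error.

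**The case against.** The strongest reply is that little depends on this. The factor 100 looks like a carry-over from the compliance formula. It applies equally to both arms and both periods, so ratios and the relative comparison of arms are untouched, and a mean of 300 drops/day would probably be caught when the tables are checked. The missing eye is an omission, not an instruction to sum both eyes. Both Table 3 rows cite the same eCRF form, and SAP 7.1 says some endpoints will be analysed on the eligible eye, so the eligible eye is a natural reading. The extra day matters by less than 2% for anyone followed to week 12. The tables are descriptive, and the models in SAP 10.1.2 and 10.2.2 do not include tear use.

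All of that stands as a limit on the consequence. It does not remove the defect: the unit and the formula contradict each other, the follow-up dates do not match, and no other section corrects either or names the follow-up eye. SAP 7.1 leaves such details to output notes and does not settle this row.

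A reader might go further and infer that the formula error is what makes treatment and follow-up use incomparable as rescue lubrication. The documents do not support that. Tears are as-needed in one period and scheduled for 8 weeks of the other, so the periods differ by design even after correction. No treatment-versus-follow-up test is planned. A reader might also take these tables as the only record of supplementary lubrication. They are not: concomitant ophthalmic medications are tabulated (SAP 8.6), and tear use is listed by patient (Listing 16.2.5.3).

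**Conclusion.** The point holds as a correctable error in the rules for two descriptive tables. Followed exactly, they would print values 100 times the stated unit. Follow-up would be a further 1.8% too low for a patient last assessed at week 12, or about twice as high if both eyes are summed. The figures rest on nominal visit days and a constant 3 drops/day/eye. The under-2% size of the day mismatch applies to patients assessed at week 12 or later; for one last assessed at week 8 (day 56) it is 1 / (56 − 28 + 1) = 1/29 = 3.4%.

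It would be wrong to infer that comparisons between arms or the efficacy conclusions are biased. The same rules apply to both arms: absolute differences carry the factor 100, while relative ones do not. No primary or key secondary test uses these values. A round 600 for both eyes does not follow from the SAP either. The treatment row allows only the eligible eye, and the follow-up row with its extra day gives 589.5 or 595.7. Pooling all of follow-up is a choice that could be improved, not a mistake.

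**What to change.** In SAP 9.3, delete the multiplication by 100 from both formulas so that the result is in drops per day. In SAP Table 3, restrict the follow-up drop count to the eligible eye, as the treatment row already does, and remove the +1 from the follow-up days so that numerator and denominator both start on the day after End of Treatment.

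As a cheap addition, summarise follow-up separately for weeks 5-12, when tears are scheduled three times daily and which precede the week 12 SANDE assessment, and for weeks 13-24. The protocol's schedule already records tear-use frequency at weeks 8, 12, 16 and 24.

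The cost is a few words in the SAP and a few lines of programming. On the documents available, data collection, patient management and the efficacy analyses are unchanged.

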5. STUDY MEDICATION

5.1. DESCRIPTION OF PRODUCT

5.1.1. Presentation of Non Investigational Medicinal Product (NIMP)

TEST PRODUCT

NIMP

Blink® Tears or equivalent preservative-free artificial tears

Pharmaceutical form

Lubricating Eye Drops

Administration

One drop of Blink® Tears or equivalent will be instilled in both eyes during the screening week, only if strictly needed by the patient. The patient must document in the patient's diary the n° of additional drops administered for each eye.

One drop of Blink® Tears or equivalent will be instilled in both eyes during the 4 weeks of masked treatment, only if strictly needed by the patient. The patient must document in the patient's diary the n° of additional drops administered for each eye.

One drop of Blink® Tears or equivalent will be instilled in both eye TID (morning, afternoon and evening) during the initially 8 weeks of follow up. The patient, only if strictly needed, can administer additional drops and must document in the patient's diary the n° of additional drops administered for each eye.

Administration route

Ocular

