6.2. STUDY VISITS AND FOLLOW-UP ASSESSMENTS

After the first two weeks of treatment the patient will undergo a medical assessment during the visit 2 (week 2). Following the completion of the double-blind treatment (visit 3, week 4), patients will be followed up for efficacy until visit 6 (week 16) and safety assessments until visit 7 (week 24). During the follow-up period until

week 12 patients will not use further ophthalmic treatment except preservative free artificial tears, provided by Sponsor, one drop instilled in both eyes three times daily (morning, afternoon and evening). The patient, only if strictly needed, can administer additional drops and must document in the patient's diary the n° of additional drops administered for each eye. After week 12 (visit 5), patients will be followed-up for additional 12 weeks until the end of the study (visit 7, week 24) during which patients can use others artificial tears different from the artificial tears provided by the Sponsor.

Slit lamp examination and the fluorescein staining (Corneal and/or Conjunctival staining with Fluorescein) will be performed at different time-points, as specified in the section 2 of "SCHEDULE OF EVALUATIONS" and procedure will be detailed on the informed consent form.

An independent Blinded Reading Center will also be used to assess the images collected, as described in the previous paragraph.

	Day	Procedures/Assessments
At home	Days 1-14 ±2	
 ➤ Self-administration at home of the IMP, three times daily every 6 h for both eyes (diary) ➤ Recording any new or changes in concomitant medications (diary) ➤ Recording any unusual medical conditions - AE monitoring (diary) ➤ Recording possible use of preservative free artificial tears (diary). 
Data will be recorded by the patient in the patient's diary.

	Day	Procedures/Assessments

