Visit 5 Follow up week 12	Day 84 ± 4	
The following procedures will be performed (the below order is mandatory):
 
 ➤ Ocular examination of both eyes to be performed by the physician investigator: 
 • Assessment by SANDE questionnaire • Assessment by IDEEL questionnaire • Assessment of best corrected distance visual acuity (BCDVA) • External Ocular Examination • Schirmer test I (without anesthesia) • Slit-lamp examination (SLE) to assess the Eyelid - Meibomian glands, Eyelid – Erythema, Eyelid - Edema Lashes, Conjunctiva Erythema, Lens, Iris, Anterior Chamber, Corneal Horizontal Diameter • TFBUT • Ocular surface staining (NEI score - corneal and conjunctival fluoresce instaining) ➤ Concomitant ocular and systemic medications ➤ Frequency of patient's artificial tear use during 4 weeks of FU (to be reported in eCRF). ➤ AE monitoring 
During visit 5, week 12, PI or delegate must check and collect the patient's diary concerning the follow up period and provide a new diary for the second follow up period.
 
The Investigator will instruct the patient that during the follow up period (from week 13 to week 24) other topical treatments will be allowed at discretion of the treating physician. Such treatments will be recorded by the investigators.
 
The patient has to register the use other preservative free artificial tears in the patient's diary.

At home	Days 84 ± 4 – 168 ± 7	
 ➤ Recording any new or changes in concomitant medications (diary) ➤ Recording any unusual medical conditions - AE monitoring (diary) ➤ Artificial tears use during 4 weeks of FU (diary) 
Data will be recorded by the patient on the patient's diary.

	Day	Procedures/Assessments

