Table 14.3.1.5	Summary of Serious TEAEs by Primary SOC and PT and by study period	SAF		X
Table 14.3.1.6	Summary of ADRs by Primary SOC and PT and by study period	SAF		X
Table 14.3.1.7	Summary of ADRs by Primary SOC and PT and Severity	SAF		X

Number	Title	Population	KFR	Final Analysis
Table 14.3.1.8	Summary of TEAEs leading to IMP Discontinuation by Primary SOC and PT and by study period	SAF		X
Table 14.3.1.9	Summary of TEAEs leading to study Discontinuation by Primary SOC and PT and by study period	SAF		X
Table 14.3.1.10	Summary of TEAEs leading to Death by Primary SOC and PT	SAF		X
Table 14.3.2.1.1	Compliance to IMP	FAS		X
Table 14.3.2.1.2	Compliance to IMP	SAF		X
Table 14.3.2.2.1	Extent of exposure to IMP	FAS		X
Table 14.3.2.2.2	Extent of exposure to IMP	SAF		X
Table 14.3.2.3.1	Use of preservative free artificial tears by study period	FAS		X
Table 14.3.2.3.2	Use of preservative free artificial tears by study period	SAF		X

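### The SAP's single follow-up tear-use rate mixes the regimen before week 12 with the one after it, so no planned table shows tear use by arm in weeks 5-12

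*SAP*

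**What the plan says.** SAP 9.3 summarises preservative-free tear use by treatment group, "by study period (treatment / follow-up) and overall according to the following formulas". The inputs are in SAP 12.1, Table 3.

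- **Follow-up numerator:** "Sum of Morning/Afternoon/Evening Number of drops taken after End of Treatment date". It has no upper time limit and names no eye.
- **Follow-up denominator:** "Last follow-up available visit* date – End of Treatment date + 1", where the last visit is the last one with a tear-use assessment.
- **Treatment-period numerator, for comparison:** "Number of drops taken for eligible eye between Randomization visit date and End of Treatment date".

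The output is "Use of preservative free artificial tears by study period" (SAP 15.1, Table 14.3.2.3.1 for the FAS and 14.3.2.3.2 for the safety set).

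The protocol sets two regimens within follow-up. Up to week 12 the sponsor's tears "will be instilled in both eye TID (morning, afternoon and evening) during the initially 8 weeks of follow up" (Protocol 5.1.1), with extra drops if strictly needed. After week 12, "patients can use others artificial tears different from the artificial tears provided by the Sponsor" (Protocol 6.2), and "during the follow up period (from week 13 to week 24) other topical treatments will be allowed at discretion of the treating physician" (Protocol 6.2, week 12 visit). Protocol 2 and 6.2 collect tear use for the eCRF at weeks 8, 12, 16 and 24.

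**The concern.** The symptom co-primary is the change in global SANDE at week 12. Lubricant taken as needed can relieve the symptoms that SANDE measures. The estimand is treatment policy, so SANDE values are used whatever else the patient took. A reader of the result will therefore ask whether tear use differed by arm in the eight weeks between end of treatment and that assessment.

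The planned table does not answer this. Its follow-up rate runs on to week 24, and drops used after week 12 cannot have influenced the week 12 score. The other medication summaries do not fill the gap: SAP 8.6 counts subjects by drug class, not drops by period.

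**Working it through.** The plan gives no figure for tear use to reproduce. Its power figures (SAP 5) do reproduce with 45 evaluable patients per arm at one-sided 0.025:

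- Schirmer, 5% versus 35%, pooled variance: 95.8%.
- SANDE, 15 points with SD 20, noncentral t with 88 df: 94.0%.
- Product: 0.958 × 0.940 = 0.90.

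Tear use enters none of these.

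**Inputs** (Protocol 2; SAP 4.4): end of treatment day 28 ± 2, week 12 day 84 ± 4, week 16 day 112, week 24 day 168 ± 7. The multiplication by 100 in SAP 9.3 is left out, because the stated unit is drops per day.

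**Formula.** Let r1 be the mean drops/day from end of treatment to week 12, and r2 the mean after week 12.

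- Days after end of treatment up to week 12: 84 − 28 = 56.
- Days after week 12 up to week 24: 168 − 84 = 84.
- Table 3 denominator: 168 − 28 + 1 = 141.
- Rate = (56·r1 + 84·r2)/141 = 0.40·r1 + 0.60·r2.

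**Weight of weeks 5-12, by last visit with tear data:**

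| Last tear-use visit | Denominator (days) | Weight of weeks 5-12 |
|---|---|---|
| Week 12 | 84 − 28 + 1 = 57 | 56/57 = 0.98 |
| Week 16 | 112 − 28 + 1 = 85 | 56/85 = 0.66 |
| Week 24 | 141 | 56/141 = 0.40 |

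The weight thus depends on how long each patient is followed.

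**Visit windows, follow-up to week 24, treatment ended on schedule:**

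- Lowest: (80 − 30)/(175 − 30 + 1) = 50/146 = 0.34.
- Highest: (88 − 26)/(161 − 26 + 1) = 62/136 = 0.46.

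**Illustration.** The documents give no expected tear use or arm difference, so these differences are assumed.

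- A difference of 1 drop/day in weeks 5-12 and none later: 56 × 1/141 = 0.40.
- No difference in weeks 5-12 and 56/84 = 0.67 drops/day later: 84 × 0.67/141 = 0.40, the same printed value.
- +1 in weeks 5-12 and −0.67 later: the two cancel to 0.

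The pooled figure therefore cannot be converted back into a weeks 5-12 difference.

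**The case against.** The strongest reply is that the consequence is small. Tear use is neither an endpoint nor a covariate, and the table is descriptive. Patient-level use is in Listing 16.2.5.3, and SAP 7.1 allows post-hoc tables, so the split could be made later. All of this stands, and it limits the point to interpretation. What remains is that a split specified before unblinding is better evidence than one chosen afterwards, and it costs almost nothing.

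Four stronger readings are tempting, and the documents do not support them.

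- **That the table shows nothing about tear use before the week 12 SANDE.** Weeks 1-4 also precede it, and the same table reports them by arm for the eligible eye.
- **That the unnamed eye is why the arms cannot be compared.** The missing split at week 12 is the reason. Scheduled tears go into both eyes in both arms, and SANDE has one frequency line and one severity line per patient (SAP 12.2). The missing eye is a drafting ambiguity.
- **That recorded drops are known to include, or to leave out, the three scheduled ones.** Protocol 5.6 points to total use per day; Protocol 5.1.1 and 6.2 speak of documenting additional drops. The diary and eCRF are not among the documents, so this is a point to confirm.
- **That the co-primary analysis is biased.** Nothing in the tear-use derivation enters the SANDE model or its imputation.

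**Conclusion.** The point holds as a minor one. The follow-up rate averages two regimens that the protocol itself separates at week 12, and no table listed in SAP 15.1 isolates tear use by arm in weeks 5-12. For a patient followed to week 24, those weeks carry 0.40 of the rate, so most of the weight falls on days after the co-primary assessment.

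The 0.40 rests on nominal visit days, and the 0.34 to 0.46 range on treatment ending within its visit window. Patients who stop study drug early but stay in the study may have an earlier end-of-treatment date and fall outside that range. The 1 drop/day difference shows the dilution and is not a forecast.

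Two smaller slips sit in the same formulas. Multiplying by 100 does not give the drops/day that SAP 9.3 announces. The added day counts the end-of-treatment day in the denominator, although the numerator starts after it.

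**What to change.** In SAP 9.3, Table 3 and Tables 14.3.2.3.1 and 14.3.2.3.2, replace the single follow-up rate with two rates for the eligible eye, in drops/day and without the factor of 100:

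- **(a) End of treatment to week 12:** drops after the end-of-treatment date up to the week 12 visit, divided by those days.
- **(b) After week 12:** drops after the week 12 visit up to the last visit with tear data, divided by those days.

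Label (a) by its end points and not as weeks 5-12, because early stoppers may enter it before week 5. If the week 12 visit is missed, end (a) at the last earlier visit with tear data, or split dated diary or eCRF records at day 84; choose the rule before lock. At the blind data review meeting, confirm from the diary and eCRF whether recorded drops include the three scheduled ones, and footnote the tables accordingly.

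The cost is a short SAP edit and a few extra rows in two descriptive tables. It needs no new data, no protocol amendment and no change to any inferential analysis.
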